7.3. Clinical Laboratory Tests

All clinical laboratory test results outside of the reference range will be interpreted by the investigator as belonging to 1 of the following categories:

- abnormal but not a clinically significant worsening from baseline
- abnormal and a clinically significant worsening from baseline

A laboratory test result that has significantly worsened (according to medical judgment) from the baseline result will be recorded on the source documentation, transcribed onto the CRF as an adverse event, and monitored as described in Section 7.1.2. An adverse event includes a laboratory or diagnostic test abnormality (once confirmed by repeat testing) that results in the withdrawal of the patient from the study, the temporary or permanent cessation of treatment with study drug, or medical treatment or further diagnostic work-up.

In addition, potentially clinically significant values will be predefined by the sponsor for selected laboratory parameters and will be detailed in the statistical analysis plan.

Clinical laboratory tests (serum chemistry, hematology, coagulation, and urinalysis) will be performed at the time points detailed in [Table 1](#) (patients rolling over from the pivotal efficacy studies) and [Table 2](#) (patients not rolling over from the pivotal efficacy studies). Clinical laboratory tests will be performed using the central laboratory. Specific laboratory tests to be performed are listed below.

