7.3.1. Serum Chemistry

The following serum chemistry tests will be performed:

- calcium
- phosphorus
- sodium
- potassium
- chloride
- carbon dioxide
- magnesium
- glucose
- blood urea nitrogen
- creatinine
- ALT
- AST
- total bilirubin
- direct bilirubin
- indirect bilirubin (calculated)
- lactate dehydrogenase
- GGT
- ALP
- albumin
- creatine phosphokinase
- total protein

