7.3.3. Coagulation

The following coagulation tests will be performed:

- prothrombin time
- partial thromboplastin time
- INR

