9.7.2. Safety and Tolerability Analysis

All adverse events will be coded using the Medical Dictionary for Regulatory Activities. Each patient will be counted only once in each preferred term or system organ class category for the analyses of safety. Summaries will be presented for all adverse events (overall and by severity), adverse events determined by the investigator to be related to study treatment (ie, reasonable possibility; see [Section 7.1.4](#)) (defined as related or with missing relationship) (overall and by severity), serious adverse events, and adverse events causing withdrawal from the study. Patient listings of serious adverse events and adverse events leading to withdrawal will be presented.

Injection site erythema, induration, ecchymosis, and pain will be assessed, and severity will be graded as described in [Section 7.9](#), and findings will be listed and summarized.

Changes in laboratory and vital signs measurement data will be summarized descriptively. All values will be compared with prespecified boundaries to identify potentially clinically significant changes or values, and such values will be listed.

The use of concomitant medications will be summarized by therapeutic class using descriptive statistics. Concomitant medications will include all medications taken while the patient is treated with study drug.

Safety data will be summarized descriptively overall, by diagnosis, and by treatment group. For continuous variables, descriptive statistics (n, mean, SD, median, minimum, and maximum) will be provided for actual values and changes from baseline to each time point. For categorical variables, patient counts and percentages will be provided. Descriptive summaries of serious adverse events, patient withdrawals due to adverse events, and potentially clinically significant abnormal values (clinical laboratory or vital signs) based on predefined criteria will also be provided.

If any patient dies during the study, a listing of deaths will be provided and all relevant information will be discussed in the patient narrative included in the clinical study report.

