- Should the abnormality ($\geq 3\times$ the ULN in case baseline was within the normal range or $\geq 2\times$ the ULN in case the baseline value was above ULN but still $<5\times$ the ULN) persist further, the patient will be followed according to the investigator's discretion, but a blood sample for ALT, AST, GGT, ALP, and total and direct bilirubin should be sent to the central laboratory at least once a month.

ALT or AST $\geq 5\times$ but Less Than $8\times$ the ULN

In addition to the above procedures required for any elevation to levels $>3\times$ the ULN:

- Alanine aminotransferase, AST, GGT, ALP, total and direct bilirubin, CBC and differential count (to assess for eosinophilia), and INR should be monitored twice a week.
- At least for every other measurement, the tests should be sent to the central laboratory. The rest of the tests may be sent to a local laboratory. The INR should always be sent to a local laboratory.

ALT or AST $\geq 8\times$ the ULN

In addition to the above procedures required for any elevation to levels $>3\times$ the ULN:

- The study drug should be discontinued immediately, and the early withdrawal visit should be performed.
- For follow-up guidance, please see below section “Follow-Up of Liver Enzymes After Stopping Rules Are Met.”

Stopping Rules

In the following circumstances, the study drug will be discontinued immediately:

- any increase in ALT or AST to $\geq 3\times$ the ULN, combined with INR $>1.5\times$ the ULN or total bilirubin $>2\times$ the ULN
- any increase in ALT or AST to $\geq 3\times$ the ULN, which is accompanied by symptoms clearly associated with impaired liver function (eg, vomiting, nausea, fever, rash, eosinophilia) and not deemed related to other diseases (eg, vomiting or nausea triggered by migraine)
- any increase in ALT or AST to levels ≥ 5 but $<8\times$ the ULN, which is persistent for ≥ 2 weeks of repeated measurements
- any increase in ALT or AST to levels $\geq 8\times$ the ULN
- in any case where monitoring of liver enzymes cannot be performed according to the protocol guidance

Follow-Up of Liver Enzymes After Stopping Rules Are Met

- A patient who meets the above criteria for discontinuation of the study drug should be invited to the site to return the study drug. Early withdrawal visit activities should be performed as soon as possible.
- Liver enzymes should be monitored until normalization or stabilization of the abnormality, according to the discretion of the investigator.

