7.6. Clinical Laboratory Tests

Clinical laboratory tests (serum chemistry, hematology, coagulation, and urinalysis) will be performed at the time points detailed in [Table 1](#) and [Table 2](#) using the central laboratory. Specific laboratory tests to be performed are listed below in [Table 6](#).

Table 6: Clinical Laboratory Test

Serum chemistry	Hematology	Coagulation	Urinalysis

 • calcium • phosphorus • sodium • potassium • chloride • carbon dioxide • magnesium • glucose • blood urea nitrogen • creatinine • ALT • AST • total bilirubin • direct bilirubin • indirect bilirubin (calculated) • lactate dehydrogenase • GGT • ALP • albumin • creatine phosphokinase • total protein 	
 • hemoglobin • hematocrit • RBC count • RBC indices 
 - mean corpuscular volume - mean corpuscular hemoglobin concentration - RBC distribution width • platelet count • WBC count and differential count (absolute values and percentages) 
 - neutrophils - lymphocytes - eosinophils - monocytes - basophils 	
 • prothrombin time • partial thromboplastin time • INR 	
 • color and appearance • specific gravity • pH • blood (hemoglobin) • glucose • albumin • protein • ketones • leukocyte esterase • nitrite • direct bilirubin • microscopic 
 - bacteria - RBCs - WBCs - casts - crystals

Laboratory tests results and changes from baseline for chemistry, hematology, urinalysis, and coagulation laboratory tests will be summarized by visits for each treatment group using descriptive statistics. Shifts (below, within, and above the normal range) from baseline to each visit and endpoint will be summarized using patient counts.

The incidence of potentially clinically significant abnormal results will be summarized using descriptive statistics with the criteria specified in [Table 7](#). The potentially clinically significant abnormal laboratory values will include all postbaseline values (including scheduled, unscheduled, and early termination visits) for the summaries. Listings of patients who have potentially clinically significant abnormal laboratory data will be presented.

Table 7: Criteria for Potentially Clinically Significant Laboratory Values

Test	Criterion value
Serum chemistry	
ALT	$\geq 3 \times \text{ULN}$
AST	$\geq 3 \times \text{ULN}$

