ALP	$\geq 3 \times \text{ULN}$
GGT	$\geq 3 \times \text{ULN}$
Lactate dehydrogenase	$\geq 3 \times \text{ULN}$
Blood urea nitrogen	$\geq 10.71 \text{ mmol/L}$
Creatinine	$\geq 177 \mu\text{mol/L}$
Uric acid Men	$\geq 625 \mu\text{mol/L}$
Women	$\geq 506 \mu\text{mol/L}$
Bilirubin (total)	$\geq 34.2 \mu\text{mol/L}$
Hematology	
Hematocrit Men	$< 0.37 \text{ L/L}$
Women	$< 0.32 \text{ L/L}$
Hemoglobin Men	$\leq 115 \text{ g/L}$
Women	$\leq 95 \text{ g/L}$
WBC counts	$\leq 3 \times 10^9/\text{L}$ or $\geq 20 \times 10^9/\text{L}$
Eosinophils	$\geq 10\%$
Absolute neutrophil counts	$\leq 1 \times 10^9/\text{L}$
Platelet counts	$\leq 75 \times 10^9/\text{L}$ or $\geq 700 \times 10^9/\text{L}$
Urinalysis	
Blood (HGB)	≥ 2 unit increase from baseline
Glucose	≥ 2 unit increase from baseline
Ketones	≥ 2 unit increase from baseline
Total protein	≥ 2 unit increase from baseline

ALP=alkaline phosphatase; ALT=alanine aminotransferase; AST=aspartate aminotransferase; GGT=gamma-glutamyl transpeptidase; HGB=hemoglobin; INR=international normalized ratio; ULN=upper limit of normal range; WBC=white blood cell

Serum beta-human chorionic gonadotropin (β -HCG) tests will be performed for all women of childbearing potential at screening (visit 1), and urine β -HCG tests will be performed for women of childbearing potential at visits 2 through 5. Positive pregnancy test results will be listed.

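### SAP Table 7 sets limits for uric acid, which is in neither laboratory panel, and none for INR or any coagulation test, so an isolated raised INR is missing from the potentially clinically significant summary and listing

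*SAP*

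**What the plan says.** SAP 7.6 states: "The incidence of potentially clinically significant abnormal results will be summarized using descriptive statistics with the criteria specified in" Table 7. No other laboratory PCS criteria are given. Table 7 has a chemistry, a hematology and a urinalysis block, and uric acid has separate limits for men and women. There is no coagulation block, yet the footnote expands an abbreviation that the table never uses: "HGB=hemoglobin; INR=international normalized ratio; ULN=upper limit of normal range".

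The tests themselves are fixed elsewhere. Protocol 7.3.1 gives the chemistry list ("The following serum chemistry tests will be performed") and Protocol 7.3.3 the coagulation list ("The following coagulation tests will be performed"): prothrombin time, partial thromboplastin time and INR. SAP 7.6 repeats the panels ("Specific laboratory tests to be performed are listed below in" Table 6).

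The protocol describes the PCS review in two ways. Section 7.3 says that "potentially clinically significant values will be predefined by the sponsor for selected laboratory parameters". Section 9.7.2 says: "All values will be compared with prespecified boundaries to identify potentially clinically significant changes or values, and such values will be listed". SAP section 13 declares no changes to the protocol-specified analyses.

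**The concern.** Laboratory change is part of the study's primary (safety) endpoint set, and coagulation is named in it beside chemistry, hematology and urinalysis (Protocol 2.3.4, SAP 2.2.4). The PCS table is the only laboratory output that applies a fixed limit and uses every postbaseline value, including unscheduled and early-termination visits. One of the four parts of the endpoint is wholly absent from it, while space is given to a test that the study does not plan to run.

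INR matters most here. Protocol 1.4.1.1 lists liver enzyme elevation as a potential risk, and INR is one limb of the protocol's liver-injury criterion. The other limbs (ALT, AST and total bilirubin) all have Table 7 rows. At stake is whether a raised INR without a marked transaminase rise would show in the output designed to display outlying values.

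**Working it through.** No sample-size or power arithmetic applies. The check is a match of tests to limits, followed by a trace of where a raised INR would be reported.

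**1. Table 7 against the panels**

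- Tests in Table 7: 9 chemistry + 6 hematology + 4 urinalysis = 19.
- Tests also in SAP Table 6: 18. The exception is uric acid.
- Protocol 7.3.1 and SAP Table 6 list the same 21 chemistry tests, and uric acid is in neither. As planned, its two rows cannot be filled.

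**2. The panels against Table 7**

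- Chemistry tests with a limit: 9 − 1 = 8 of 21.
- Coagulation tests with a limit: 0 of 3.
- INR: no criterion row, one footnote mention.

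**3. Where a raised INR goes**

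Take an INR above the liver threshold.

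- *With ALT or AST ≥3 × ULN in the laboratory data.* Table 7 has ALT and AST rows at ≥3 × ULN with no baseline condition. The patient is already in the PCS incidence table and listing, through the transaminase row.
- *With ALT and AST below 3 × ULN.* No Table 7 row captures the INR. Three other routes remain:
  - By-visit summaries of coagulation results and changes (SAP 7.6), which include the maximum (SAP 4.1).
  - Shift tables of below, within or above normal (SAP 7.6). These cannot separate a value past the liver threshold from one just above normal.
  - Adverse events. Under Protocol 7.3 the investigator classifies every out-of-range result. SAP 7.3 summarizes and lists protocol-defined events, which include possible liver injury. This route depends on a report and is not a programmed check of the laboratory data.

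The first two routes share a weakness. SAP 4.6 keeps the last non-missing assessment at a visit, counting unscheduled ones. A high INR followed by a normal repeat assigned to the same visit drops out of both the shift count and the by-visit maximum. SAP 4.6 also excludes early-termination safety data from by-visit summaries, although they enter the endpoint summary. A PCS row would keep both values.

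**4. The INR limit as the documents word it**

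- Protocol 7.1.1: AST or ALT ≥3 × ULN, plus either total bilirubin ≥2 × ULN or INR >1.5. INR counts only jointly.
- Protocol 7.1.6 and SAP 7.3: the same figures without the words that join the two parts, so INR >1.5 could be read as sufficient alone.
- Protocol Appendix E, Stopping Rules: ALT or AST ≥3 × ULN "combined with INR" >1.5 × the ULN, or with raised total bilirubin.

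If the laboratory's upper INR limit is U, the two INR limits differ by 1.5U − 1.5 = 1.5(U − 1). They agree only if U = 1. The documents give no INR reference range, so the gap cannot be evaluated.

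**The case against.** The strongest reply is that selection was announced. Protocol 7.3 promises limits for selected parameters only, and 21 − 8 = 13 chemistry tests, among them sodium, potassium and calcium, also have none. Read literally, Protocol 9.7.2 would require limits for all of them, so singling out coagulation could look like preference. This partly stands: the omission conflicts with 9.7.2 but not clearly with 7.3. Coagulation still differs from the other gaps, because a whole named part of the endpoint has no limit and because INR is the only limb of the liver criterion left out. A selection that includes a test outside the panel also does not look checked against this study, and SAP section 13 records no departure.

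The second reply is that INR >1.5 is not a stand-alone limit where the protocol states it in full, and that the combined criterion is already covered by the ALT and AST rows. This stands, and it confines the gap to an isolated raised INR. If the looser wording of Protocol 7.1.6 and SAP 7.3 is taken instead, such a value is itself a protocol-defined event and is summarized and listed, but only if a site reports it.

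The third reply is that an unused footnote abbreviation proves nothing. Agreed: it is consistent with a dropped row but does not establish one. It shows only that table and footnote do not match.

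**Conclusion.** Table 7 is wrong as written: it has one test with limits and no planned data, and three planned coagulation tests with no limits. The consequence is that an INR above the liver threshold, without ALT or AST ≥3 × ULN, is missing from the PCS incidence table and listing. The number of patients this would affect cannot be estimated, because the documents give no INR distribution. The empty uric acid rows bias nothing; removing them is clean-up. The edit is worth making before the final analysis, but it does not threaten the study's conclusions.

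Two stronger readings are not supported:

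- A reader might infer that a raised INR is never flagged or counted. It can appear in by-visit summaries, shift counts and reported events.
- A reader might multiply six on-treatment laboratory visits by 1842 patients (6 × 1842 = 11,052) and say that this many INR results meet no boundary. That is a full-attendance maximum despite the anticipated 30% drop-out, and the results are still compared with the normal range.

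The conclusion assumes that Table 7 and the panels are complete as reproduced. The statement that shift tables would show the value assumes that the laboratory's upper INR limit lies below the liver threshold. INR follow-up after a transaminase rise goes to local laboratories (Appendix E), and SAP 7.6 refers only to the central laboratory, so those values may not reach the shift tables.

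**What to change.** In SAP Table 7:

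- Add a coagulation block with an INR row, marked as a reporting flag only, with no effect on stopping rules or patient management.
- Before setting its value, have the sponsor reconcile the INR limit between Protocol 7.1.1, Protocol 7.1.6 and SAP 7.3 on one side and Appendix E on the other, including whether INR counts alone or only with a transaminase rise. This review takes no position on which is right.
- Add prothrombin time and partial thromboplastin time limits if the sponsor has standard ones.
- Remove the two uric acid rows, or add uric acid to Table 6 if it is in fact assayed.
- State whether local-laboratory INR values recorded in the CRF count toward the flag.

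If the sponsor prefers to leave coagulation out of the PCS review, SAP section 13 should say so, since Protocol 9.7.2 reads otherwise. The cost is a few table rows, a sentence or two of SAP text and minor programming. No new data are needed.

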7.7. Vital Signs

Vital signs (pulse, systolic and diastolic blood pressure, body temperature, and respiratory rate) will be measured before other assessments (eg, blood draws and administration of questionnaires) at the time points detailed in [Table 1](#) and [Table 2](#).

For any abnormal vital sign finding, the measurement should be repeated as soon as possible. Any vital sign value that is judged by the investigator as a clinically significant change (worsening) from a baseline value will be considered an adverse event.

Vital signs values and changes from baseline to each visit and endpoint will be summarized using descriptive statistics. The incidence of potentially clinically significant abnormal values will be summarized for selected vital signs using descriptive statistics.

[Table 8](#) specifies the criteria for identifying vital signs as potentially clinically significant abnormal. Note that in order to be identified as potentially clinically significant abnormal, a value would need to meet both conditions below: ie, have a value beyond the criterion value and a change of at least the magnitude specified in the change from baseline column. Summaries of potentially clinically significant abnormal vital signs values will include all postbaseline values (including scheduled, unscheduled, and early termination visits).

Table 8: Criteria for Potentially Clinically Significant Vital Signs

Vital Sign	Criterion value	Change relative to baseline
Pulse	≥ 120 bpm	Increase of ≥ 15 bpm
	≤ 50 bpm	Decrease of ≥ 15 bpm
Systolic blood pressure	≥ 180 mm Hg	Increase of ≥ 20 mm Hg
	≤ 90 mm Hg	Decrease of ≥ 20 mm Hg
Diastolic blood pressure	≥ 105 mm Hg	Increase of ≥ 15 mm Hg
	≤ 50 mm Hg	Decrease of ≥ 15 mm Hg
Respiratory rate	< 10 breaths/min	
Body temperature	$\geq 38.3^\circ\text{C}$	Change of $\geq 1.1^\circ\text{C}$

A listing for clinically significant abnormal vital signs will be presented.

7.8. Electrocardiography

Twelve-lead ECGs will be conducted before other assessments (eg, blood draws and administration of questionnaires) at the time points detailed in [Table 1](#) and [Table 2](#).

Any ECG finding that is judged by the investigator as a potentially clinically significant change (worsening) compared with the baseline value will be considered an adverse event.

Shifts (normal and abnormal) from baseline to end of treatment will be summarized using patient counts and percentages. For overall, the worst post baseline finding (the abnormal finding if there are both normal and abnormal findings) for the patient will be summarized. Electrocardiogram variables results and changes from baseline to each visit and endpoint will be summarized using descriptive statistics.

7.9. Physical Examinations

Physical examinations, including height (to be obtained at the screening visit only) and weight will be performed at the time points detailed in [Table 1](#) and [Table 2](#).

A complete physical examination will include the following organ systems: general appearance; head, eyes, ears, nose, and throat; chest and lungs; heart; abdomen; musculoskeletal; skin; lymph nodes; and neurological. Any physical examination finding that is judged by the investigator as a potentially clinically significant change (worsening) compared with a baseline value will be considered an adverse event.

Abnormal physical examination findings will be listed.

7.10. Electronic Columbia-Suicide Severity Rating Scale (eC-SSRS)

The eC-SSRS will be used to assess the patient's suicidal ideation (severity and intensity) and behavior ([Posner et al 2011](#)). The eC-SSRS Baseline/Screening version will be completed by the patient at visit 2, and the eC-SSRS Since Last Visit version will be completed by the patient at all other time points, as described in [Table 1](#) and [Table 2](#). Any positive findings on the eC-SSRS Since Last Visit version requires evaluation by a physician or doctoral-level psychologist.

Patients having positive findings will be listed.

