- to evaluate the efficacy of sc TEV-48125 in patients with migraine, as assessed by the reduction in the number of migraine days in patients not receiving concomitant migraine preventive medications at baseline
- to evaluate the efficacy of sc TEV-48125 in patients with migraine, as assessed by the reduction in the number of headache days of at least moderate severity in patients not receiving concomitant migraine preventive medications at baseline
- to evaluate the efficacy of sc TEV-48125 in patients with migraine, as assessed by the reduction in the number of migraine days for new patients and placebo-treated rollover patients
- to evaluate the efficacy of sc TEV-48125 in patients with migraine, as assessed by the reduction in the number of headache days of at least moderate severity for new patients and placebo-treated rollover patients
- to evaluate the efficacy of sc TEV-48125 in patients with migraine, as assessed by the reduction of the number of headache days of any severity
- to evaluate the efficacy of sc TEV-48125 in patients with migraine, as assessed by the reduction of the use of any acute headache medications
- to evaluate the efficacy of sc TEV-48125 in patients with migraine, as assessed by the discontinuation of use of concomitant preventive medications
- to evaluate the efficacy of sc TEV-48125 in patients with migraine, as assessed by the reduction of migraine-related disability and change in quality of life
- to evaluate the immunogenicity of TEV-48125 and the impact of ADAs on clinical outcome in patients exposed to sc TEV-48125
- to explore the correlation between pharmacokinetic parameters and drug efficacy
- to explore the relationship between genetic polymorphisms within the CGRP receptor-ligand complex (eg, CALCA, CALCB, CALCRL, CRCP, and RAMP) and migraine-associated genes (eg, PRDM16, AJAP1, TSPAN2, MEF2D, TRPM8, TGFB2, PHACTR1, FHL5, C7orf10, MMP16, ASTN2, LRP1, APOA1BP, TBC1D7, FUT9, STAT6, ATP5B, and MTHFR) and mode-of-action-related pathways versus hypertension, migraine severity, and safety and efficacy responses

- to explore the relationship between biofluid bone, angiogenic, and inflammatory biomarkers with TEV-48125 concentrations and efficacy responses

Study Endpoints:

Primary Endpoints: The safety and tolerability endpoints for this study are as follows:

- occurrence of adverse events throughout the study

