- changes from baseline in clinical laboratory (serum chemistry, hematology, coagulation, and urinalysis) test results
- abnormal standard 12-lead electrocardiogram (ECG) findings
- changes from baseline in vital signs (pulse, systolic and diastolic blood pressure, body temperature, and respiratory rate) measurements
- abnormal physical examination findings
- abnormal local injection site tolerability findings (ie, erythema, induration, and ecchymosis) and occurrence of injection site pain
- suicidal ideation and behavior as suggested by the electronic Columbia-Suicide Severity Rating Scale (eC-SSRS)

Secondary Endpoints: There are no secondary endpoints.

Exploratory Endpoints: Exploratory endpoints are as follows:

- mean change from baseline (28-day run-in period) in the number of migraine days during the 4-week periods after visits 4, 7, and 13
- mean change from baseline (28-day run-in period) in the number of headache days of at least moderate severity during the 4-week periods after visits 4, 7, and 13
- mean change from baseline (28-day run-in period) in the number of migraine days during the 4-week periods after visits 4, 7, and 13 in patients not receiving concomitant migraine preventive medications at baseline
- mean change from baseline (28-day run-in period) in the number of headache days of at least moderate severity during the 4-week periods after visits 4, 7, and 13 in patients not receiving concomitant migraine preventive medications at baseline
- mean change from baseline (28-day run-in period) in the number of migraine days during the 4-week period after the 1st dose of study drug for new patients and placebo-treated rollover patients
- mean change from baseline (28-day run-in period) in the number of headache days of at least moderate severity during the 4-week period after the 1st dose of study drug for new patients and placebo-treated rollover patients
- mean change from baseline (28-day run-in period) in the number of headache days of any severity during the 4-week periods after visits 4, 7, and 13
- mean change from baseline (28-day run-in period) in the number of days of use of any acute headache medications during the 4-week periods after visits 4, 7, and 13

- proportion of patients reaching at least 50%, 75%, and total (100%) reduction in the number of headache days of at least moderate severity during the 4-week periods after visits 4, 7, and 13

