9.5.1. Primary Endpoint

The primary endpoints for this study are safety-related and are presented in Section 9.7.

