9.7. Safety and Tolerability Endpoints and Analysis

Safety and tolerability analyses will be performed on the safety analysis set. Summaries will be presented overall, by indication and by treatment group.

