9.7.1. Safety and Tolerability Endpoints

The safety and tolerability endpoints for this study are as follows:

- occurrence of adverse events throughout the study
- changes from baseline in clinical laboratory (serum chemistry, hematology, coagulation, and urinalysis) test results
- abnormal standard 12-lead ECG findings
- changes from baseline in vital signs (pulse, systolic and diastolic blood pressure, body temperature, and respiratory rate) measurements
- abnormal physical examination findings
- abnormal local injection site tolerability findings (ie, erythema, induration, and ecchymosis) and occurrence of injection site pain
- suicidal ideation and behavior as suggested by the eC-SSRS

Safety and tolerability measures and time points are provided in [Table 1](#) (patients rolling over from the pivotal efficacy studies), [Table 2](#) (patients not rolling over from the pivotal efficacy studies), and [Table 3](#) (patients rolling over from the pivotal efficacy studies for ADA assessment only).

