2.2.4. Safety and Tolerability Endpoints

The safety and tolerability endpoints for this study are as follows:

- occurrence of adverse events throughout the study
- changes from baseline in clinical laboratory (serum chemistry, hematology, coagulation, and urinalysis) test results
- abnormal standard 12-lead electrocardiogram (ECG) findings
- changes from baseline in vital signs (pulse, systolic and diastolic blood pressure, body temperature, and respiratory rate) measurements
- abnormal physical examination findings
- abnormal local injection site tolerability findings (ie, erythema, induration, and ecchymosis) and occurrence of injection site pain
- suicidal ideation and behavior as suggested by the electronic Columbia-Suicide Severity Rating Scale (eC-SSRS)

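### The SAP plans only a listing for the eC-SSRS, a primary endpoint, although the protocol calls for safety data to be summarised with counts and percentages by treatment group

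*SAP*

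**What the plan says.** The Protocol Synopsis introduces the list with "Primary Endpoints: The safety and tolerability endpoints for this study are as follows", and the eC-SSRS is the last of its seven items. Protocol 9.5.1 agrees: "The primary endpoints for this study are safety-related and are presented in Section 9.7". Protocol 9.7.1 then includes "suicidal ideation and behavior as suggested by the eC-SSRS". SAP 2.2.4 carries the same item: "suicidal ideation and behavior as suggested by the electronic Columbia-Suicide Severity Rating Scale".

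On presentation, Protocol 9.7 states: "Summaries will be presented overall, by indication and by treatment group". Protocol 9.7.2 adds: "Safety data will be summarized descriptively overall, by diagnosis, and by treatment group", and asks for patient counts and percentages for categorical variables. Neither section exempts the eC-SSRS.

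SAP 7.10 describes the instrument, says which version is used when, requires clinical evaluation of positive Since Last Visit results, and ends with its only output: "Patients having positive findings will be listed". It does not define a positive finding. SAP 13 records no change to the protocol's analyses. The SAP Preface says that the SAP takes precedence where the two documents differ, and that differences will be explained in the study report.

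**The concern.** A listing shows individual patients. It does not show how many patients out of how many in each regimen had ideation or behaviour, which is what the protocol's rule for categorical safety data would give. The SAP takes precedence, so a programmer working from 7.10 would produce no eC-SSRS table, and SAP 13 gives no sign that anything was dropped. At stake is whether a primary endpoint reaches the study report in the form the protocol describes, with a stated definition and a count that can be reproduced.

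**Working it through.** No sample-size or power calculation applies. The check sets the sections side by side and then tests how far the consequence reaches.

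**1. Is the eC-SSRS primary?** Yes. The Synopsis list has seven items, and the same seven appear in Protocol 9.7.1, SAP 2.2.4 and SAP 7.1.

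**2. What does the SAP specify for each of the seven?**

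| Endpoint | SAP section | Planned output |
|---|---|---|
| Adverse events | 7.3 | Incidence summaries by treatment group and overall, plus listings |
| Laboratory tests | 7.6 | Descriptive statistics, shifts, incidence of potentially clinically significant values, listing |
| ECG | 7.8 | Shifts with counts and percentages, changes from baseline |
| Vital signs | 7.7 | Descriptive statistics, incidence of potentially clinically significant values, listing |
| Physical examination | 7.9 and 5.6 | Listing in 7.9; abnormal findings summarised in 5.6 |
| Injection site | 7.4 | Number and percentage by grade, visit and treatment group |
| eC-SSRS | 7.10 | Listing only |

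The eC-SSRS is the only one of the seven for which no section names a summary.

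**3. Does a general rule fill the gap?** SAP 7.1 says that CM and EM patients will be summarised separately for their safety endpoints, with descriptive statistics by treatment group, and its endpoint list includes the eC-SSRS. The statistics sentence yields to anything specified elsewhere, and 7.10 specifies a listing. The result is an unclear plan, not a specified table.

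**4. Are denominators missing?** No. SAP 5.2 gives the size of the safety population by indication and overall, and SAP 7.2 gives the number of patients with at least one dose by treatment group. A complete listing combined with these yields n/N by hand.

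**5. Would an empty listing support an upper bound?** Yes. Planned enrolment is 867 + 675 + 300 = 1842. If all were dosed and none had a finding, the rule of three gives 3/1842 = 0.16% as a one-sided 95% upper limit. The figure is illustrative, because 1842 is planned enrolment and not a safety-population count.

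**6. Who has which eC-SSRS record at visit 2?** Under Protocol 7.7 only new patients complete the Baseline/Screening version: about 300/1842 = 16% of the plan. Rollovers (867 + 675 = 1542, or 84%) use the Since Last Visit version. By the notes to Table 1, they complete it at visit 2 only if they enter more than 30 days after visit 5 of the pivotal study. SAP 4.2 sets the rollover baseline at the pivotal-study baseline, and the safety baseline for new patients at the last value before first dose. SAP 7.10 assigns the Baseline/Screening version to visit 2 without limiting it to new patients.

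**The case against.** The best reply is SAP 7.1: it promises summaries of the safety endpoints and includes the eC-SSRS among them. That is enough to make the SAP unclear, and a sponsor could honour it. It does not say what would be counted, and the proviso lets 7.10 govern.

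A second reply is that the information survives: listing plus safety-population counts gives n/N. This is right, and it limits the concern. A reader might infer that no denominator exists, or that a listing cannot support the 0.16% bound. Steps 4 and 5 show that neither inference holds. What is missing is the tabulation itself and a definition of a positive finding.

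Third, suicidal symptoms that develop or worsen fit the adverse-event definition in Protocol 7.1.1 and, if recorded, would be tabulated under SAP 7.3. This helps only in part. SAP 7.7 to 7.9 turn clinically significant worsening in vital signs, ECG and physical examination into adverse events, but neither Protocol 7.7 nor SAP 7.10 does so for a positive eC-SSRS result.

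Fourth, SAP 7.9 also ends in a listing, which suggests a convention for sparse findings. Physical examination, however, has the summary in SAP 5.6.

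It is also fair to note that the protocol's rule is general and does not name the eC-SSRS, and that the Preface provides for explaining differences in the study report.

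**Conclusion.** The point holds as a reporting gap: the protocol's general rule calls for counts and percentages by treatment group and diagnosis, the SAP section for this primary endpoint names only a listing, and no change is declared. It affects one of seven primary endpoints. It has no bearing on sample size, power or type I error, since the trial plans no inferential analysis. The conclusion rests on reading SAP 7.1 as a layout rule that 7.10 overrides. If the sponsor reads 7.1 as binding, the defect becomes an unspecified table instead of an absent one, and the remedy is the same.

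A reader might also infer that findings present before treatment would be indistinguishable from findings on treatment. The documents do not show this. The two eC-SSRS versions have different names and are used at different visits, the listing's columns are not specified, and only about 300 planned patients complete the Baseline/Screening version. Criterion b of Protocol 4.2.2 also excludes those patients for any past suicide attempt, or for ideation with a specific plan in the past 2 years. Separate presentation is sensible, but confusion between the two is not established.

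**What to change.** Add one table to SAP 7.10, on the safety population: patients with any suicidal ideation, and patients with any suicidal behaviour, after the first dose in this study on the Since Last Visit version, as n/N (%) by treatment group, by CM/EM and overall. Keep the listing. In the same section:

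- Define a positive finding and the denominator.
- Show the visit 2 Baseline/Screening results of new patients separately, and leave pre-dose visit 2 results of late-entering rollovers out of the post-dose counts.
- If a row for new or worsened findings is wanted, limit it to patients with a usable baseline under SAP 4.2: the last pre-dose value for new patients and the pivotal-study baseline for rollovers. A visit 2 comparison for everyone would fail, because rollovers who enter within 30 days have no visit 2 eC-SSRS in this study.
- Bring the visit 2 wording into line with Protocol 7.7.

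If the sponsor prefers a listing alone, SAP 13 should declare the departure. The cost is one additional descriptive table. The post-dose data are already scheduled at visits 3 to 15; only the optional new-or-worsened row needs pivotal-study baseline data for rollovers.
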